**7.0 Visit schedule and assessments**

Table 7-1 lists all of the assessments and indicates with an “x” the visits when they are performed.

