**Table 1 Assessment schedule**

	Baseline	Week		
--	----------	------	--	--

Time Point	0	2	4	26
Visit Number	1	3	4	5
Informed Consent	X			
Background Information	X			
Inclusion/Exclusion	X			
Med Hist/Demography	X			
Vital Signs	X	X	X	X
Physical Exam	X	X	X	X
Laboratory Tests	X	X	X	X

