### **7.3 Efficacy**

The observations to assess efficacy of the investigational device include the proportion of the surgical procedure able to be performed with the device, prior to standard laparoscopic techniques that will be employed in the final surgical steps. Efficacy will be specifically measured in operative time, blood loss, and successful completion of donation. Post-operative assessments will include patient satisfaction and recovery surveys. The efficacy variables selected are standard for this indication/patient population.

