### **7.5.2 Health-related Quality of Life**

The SF-36 is a widely used instrument to measure generic health status. It is a 36-item questionnaire that yields an 8-scale health profile as well as summary measures of individual patients. It has proven useful in monitoring generic and specific populations, comparing the relative burden of different diseases, differentiating the health benefits produced by different treatments, and in screening individual patients. The purpose collecting SF-36 data in this study is to compare the final health status of those undergoing the robotic assisted single-incision laparoscopic donor nephrectomy.

The eight profiles (scales) are: bodily pain, general health, vitality, mental health, physical functioning, role-physical, role-emotional and social functioning. The two summary measures are physical health and mental health.

Patients will complete the questionnaire before other clinical assessments at any given visit. The SF-36 can be administered in 5 to 10 minutes with a high degree of respectability and quality. An appropriate person will be designated to facilitate self-administration. The administrator will not influence but will answer questions and address concerns to ensure that the questionnaire is filled out correctly and completely.

Completed questionnaires will be reviewed and examined by the investigator before the clinical examination for responses which may indicate potential AEs or SAEs. The investigator will review not only the responses to the questions in the questionnaires, but he or she will also review for any unsolicited comments written by the patient. If the occurrence of AEs or SAEs is confirmed, the physician will record the events as per instructions given in Section 7.5.1 of the protocol. Investigators will not encourage the patients to change the responses reported.

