### **10.4.2 Safety**

Safety variables to be assessed include discontinuation from study, discontinuation from treatment, renal function, AE/infection, SAE, notable events, laboratory tests, and vital signs.

Adverse events will be summarized by presenting, for each treatment group, the number and percentage of patients having any adverse event, having an adverse event in each organ system and having each individual adverse event. The same type of summaries will be provided for serious adverse events and for events suspected to be related to the study device. Any other information collected (e.g. severity or relatedness to study device) will be listed as appropriate.

Laboratory data will be summarized by baseline values to most extreme post-baseline values, by presenting summary statistics of raw data and change from baseline values (means, medians, standard deviations, ranges) and by the flagging of notable values in data listings.

Data from other tests (e.g. vital signs) will be listed, notable values will be flagged, and any other information collected will be listed as appropriate. Any statistical tests performed to explore the data will be used only to highlight any interesting comparisons that may warrant further consideration.

The data collected will be presented in listings, summary tables and graphs.

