#### **10.4.4 Health-related Quality of Life**

The change from baseline in the profile and summary scores of the SF-36 will be assessed in the treatment group.

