#### **10.7 Interim analysis**

Routine follow-up appointments will occur 2 weeks and 6 months after operation.

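### Do the missing SF-36 and survey rows in the assessment table, and a week 4 visit absent from section 10.7, call for a change to the plan?

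*Combined protocol and SAP*

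**What the plan says.** Section 7.0 introduces the visit schedule with the statement that "Table 7-1 lists all of the assessments". The table that follows is headed "Table 1 Assessment schedule". It has time points at weeks 0, 2, 4 and 26, numbered as visits 1, 3, 4 and 5. Its rows cover consent, background information, eligibility, history and demography, vital signs, physical examination and laboratory tests.

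The patient-reported measures appear only in the text:

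- Section 7.3: "Post-operative assessments will include patient satisfaction and recovery surveys". No instrument or visit is named.
- Section 7.5.2, on the SF-36: "Patients will complete the questionnaire before other clinical assessments at any given visit". The stated purpose "is to compare the final health status of those undergoing the robotic assisted single-incision laparoscopic donor nephrectomy".
- Section 10.4.4: "The change from baseline in the profile and summary scores of the SF-36 will be assessed in the treatment group".

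On follow-up, section 10.7 (under the heading Interim analysis) says: "Routine follow-up appointments will occur 2 weeks and 6 months after operation". On laboratory results, section 10.4.2 says: "Laboratory data will be summarized by baseline values to most extreme post-baseline values".

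**The concern.** A table that claims to be complete is the page site staff are most likely to work from. If they did so literally, no one would hand out an SF-36 before surgery. That score cannot be recovered afterwards, and the only SF-36 analysis in the plan is a change from baseline. Section 7.5.2 also has the investigator read the completed questionnaires for possible adverse events, so an omitted form would remove one planned safety check. The stated interest in final health status might suggest a single late administration, which would not support a change score.

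The week 4 visit raises a separate question. The table marks vital signs, examination and laboratory tests at that visit, while section 10.7 names only two follow-up appointments. If sites followed different passages, a week 4 summary could be incomplete, and the most extreme post-baseline laboratory value might be drawn from three visits in some patients and two in others.

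**Working it through.** No figure in the plan needs reproducing. The check sets the sections side by side.

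**1. Rows.** Four rows are marked at baseline only (4 × 1 = 4 marks) and three at every visit (3 × 4 = 12 marks), which gives 7 rows and 16 marks. Rows for the SF-36 or the surveys: 0 of 7. The omission is real.

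**2. Is the table meant to be exhaustive?** It also has no row for operative time and blood loss (7.3), intraoperative complications (7.4), hospitalization data (7.5.1) or adverse events (10.4.2). It works as a grid of clinic procedures. The study cannot be run from it without the text of section 7, so the word *all* in section 7.0 is loose and does not exclude what the text requires.

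**3. Can the SF-36 visits be recovered from the text?**

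- Section 7.5.2 places the questionnaire ahead of the other clinical assessments at a visit and has it reviewed before the clinical examination.
- The table marks the physical examination at weeks 0, 2, 4 and 26.
- Section 10.4.4 needs a baseline score and at least one later score.

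The natural reading is the SF-36 at each of those four visits, starting before surgery. An interest in final health status fits this, since the last visit is one of the four.

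**4. The surveys.** Section 7.3 makes them post-operative. It does not name them or say whether the recovery survey is distinct from the SF-36. Section 10 specifies no analysis of them.

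**5. Follow-up visits.**

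| Table (weeks from baseline) | Section 10.7 (from operation) |
|---|---|
| 2 | 2 weeks |
| 4 | not mentioned |
| 26 (26 × 7 = 182 days) | 6 months (365.25 / 2 ≈ 183 days) |

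One of three follow-up visits is unmatched. The matching of the other two assumes that the interval between baseline and surgery is short, and the documents do not give that interval. Section 10.7 describes routine appointments and does not say they are the only visits. Both passages hold if week 4 is a study visit in addition to routine care, although no passage states this.

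**6. The laboratory extreme.** The rule in 10.4.2 works for any number of post-baseline values and is not limited to scheduled visits. The matched-cohort comparison in 10.4.1 covers operative times, blood loss and ergonomics and does not include laboratory values, so the number of visits cannot bias a contrast between groups.

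The effect of a third visit can be given a size only with outside assumptions. For normal values with equal mean and SD at each visit and common correlation r, the expected maximum is √(1−r)/√π for two visits and 3√(1−r)/(2√π) for three. At r = 0 these are 0.564 and 0.846, a difference of 0.28 SD. At r = 0.5 the difference is 0.20 SD, and at r = 0.8 it is 0.13 SD. None of these inputs comes from the documents, and the formula reads most extreme as highest, which 10.4.2 does not say. The figures therefore carry no weight in the conclusion.

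**The case for a change.** The best case for acting is that a lost pre-operative SF-36 cannot be repaired, while adding a row to the table costs almost nothing. The phrase in 7.5.2 about any given visit can be read as fixing the order of tasks within a visit without naming the visits. Section 10.4.4 also sits under the analysis of secondary objectives, so the SF-36 is not wholly peripheral, even though section 3.2 does not list it.

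Part of this stands. The visits are nowhere listed explicitly for the SF-36, the surveys have neither a named instrument nor a visit, and no passage explains week 4. But losing the baseline score would require staff to overlook both 7.5.2 and 10.4.4. The proposed remedy would also leave the choice of follow-up visits to the sponsor. It would write down detail without altering what is measured or how it is analysed.

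The evidence has limits too. The table was read from a PDF, its label differs from the one cited in section 7.0, and visit number 2 is skipped. A lost row or column cannot be ruled out, although the rows that survive line up and section 7.1 follows directly.

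**Conclusion.** The observations are accurate, but no change to the plan follows. The missing rows are a clerical gap that the text of section 7 fills: SF-36 at the tabled clinical visits including baseline, and surveys after surgery. The week 4 difference is a point for the sponsor to reconcile when the document is next tidied. The passages are compatible as written, and nothing here says which schedule should apply.

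The size is small: 0 of 7 rows, 1 of 3 follow-up visits, 20 patients, and analyses that section 10.1 declares to be descriptive. The SF-36 change score and the laboratory summary can both be produced as stated, and an analyst would report the number of patients contributing at each visit.

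This rests on two readings: that the questionnaire instruction in 7.5.2 applies to every visit with clinical assessments, and that the routine appointments in 10.7 are not an exclusive list. Confidence is moderate, because the table may not have survived extraction intact.

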**Table 1 Assessment schedule**

	Baseline	Week		
--	----------	------	--	--

Time Point	0	2	4	26
Visit Number	1	3	4	5
Informed Consent	X			
Background Information	X			
Inclusion/Exclusion	X			
Med Hist/Demography	X			
Vital Signs	X	X	X	X
Physical Exam	X	X	X	X
Laboratory Tests	X	X	X	X

### **7.1 Information to be collected on screening failures**

Not Applicable

### **7.2 Patient demographics/other baseline characteristics**

After informed consent has been signed and the patient's eligibility to participate in the study has been determined, baseline patient information will be obtained, such as date of birth, age, sex, race, full relevant medical history/current medical conditions.

A full physical examination will be made at baseline including vital signs, blood chemistry and hematology, serum creatinine, urinalysis, including a quantitative protein/creatinine ratio.

### **7.3 Efficacy**

The observations to assess efficacy of the investigational device include the proportion of the surgical procedure able to be performed with the device, prior to standard laparoscopic techniques that will be employed in the final surgical steps. Efficacy will be specifically measured in operative time, blood loss, and successful completion of donation. Post-operative assessments will include patient satisfaction and recovery surveys. The efficacy variables selected are standard for this indication/patient population.

### **7.4 Safety**

Safety assessments include blood loss, intraoperative complications or injuries to adjacent structures, and successful completion of donation surgery. These will be

compared to center defined rates for these safety parameters. The safety assessments selected are standard for this indication/patient population.

## **7.5 Other assessments**

### **7.5.1 Resource utilization**

For resource utilization, all relevant information about initial hospitalization and all follow-up hospitalizations post procedure (in the transplant study center or all other centers, if any) will be recorded. The hospitalization data will include the main reason for admission and duration of hospitalization and length of stay. All attempts will be made to collect RU variables in all patients throughout the duration of the study in order to avoid selection bias. There may also be circumstances when the collection of such data after completion of the study may be warranted. These data will be collected in the Hospitalization CRF and will be presented in a separate report.

### **7.5.2 Health-related Quality of Life**

The SF-36 is a widely used instrument to measure generic health status. It is a 36-item questionnaire that yields an 8-scale health profile as well as summary measures of individual patients. It has proven useful in monitoring generic and specific populations, comparing the relative burden of different diseases, differentiating the health benefits produced by different treatments, and in screening individual patients. The purpose collecting SF-36 data in this study is to compare the final health status of those undergoing the robotic assisted single-incision laparoscopic donor nephrectomy.

The eight profiles (scales) are: bodily pain, general health, vitality, mental health, physical functioning, role-physical, role-emotional and social functioning. The two summary measures are physical health and mental health.

Patients will complete the questionnaire before other clinical assessments at any given visit. The SF-36 can be administered in 5 to 10 minutes with a high degree of respectability and quality. An appropriate person will be designated to facilitate self-administration. The administrator will not influence but will answer questions and address concerns to ensure that the questionnaire is filled out correctly and completely.

Completed questionnaires will be reviewed and examined by the investigator before the clinical examination for responses which may indicate potential AEs or SAEs. The investigator will review not only the responses to the questions in the questionnaires, but he or she will also review for any unsolicited comments written by the patient. If the occurrence of AEs or SAEs is confirmed, the physician will record the events as per instructions given in Section 7.5.1 of the protocol. Investigators will not encourage the patients to change the responses reported.

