**6.5.8 Study completion and post-study treatment**

At study completion CRF page should be completed after the operation. Due to the nature of the study (a onetime exposure to the investigational device during the surgical procedure) withdrawal from the study cannot occur. Subjects who wish to withdraw from the study follow up will be permitted to do so.

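### Does the misdirected adverse-event cross-reference in Section 7.5.2, with no AE or SF-36 row in the schedule, undermine the planned safety and quality-of-life summaries?

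*Combined protocol and SAP*

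**What the plan says.** Section 7.5.2 has the SF-36 completed first at each visit: "Patients will complete the questionnaire before other clinical assessments at any given visit". It then adds a safety check: "Completed questionnaires will be reviewed and examined by the investigator before the clinical examination for responses which may indicate potential AEs or SAEs". For a confirmed event, "the physician will record the events as per instructions given in Section 7.5.1 of the protocol".

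Section 7.5.1 is headed Resource utilization. On content it says "The hospitalization data will include the main reason for admission and duration of hospitalization and length of stay", and on destination "These data will be collected in the Hospitalization CRF and will be presented in a separate report".

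Section 7.4 reads: "Safety assessments include blood loss, intraoperative complications or injuries to adjacent structures, and successful completion of donation surgery". Section 10.4.2 goes further. It names adverse events and infections, serious adverse events, notable events, laboratory tests and vital signs as safety variables. It plans counts and percentages of patients with any event, by organ system and by individual event, and repeats these for serious events and for events suspected to be device-related.

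Section 7.0 introduces the schedule with "Table 7-1 lists all of the assessments". The table has columns for weeks 0, 2, 4 and 26 and seven rows: consent, background information, eligibility, history and demography, vital signs, physical examination and laboratory tests. Section 10.4.4 analyses change from baseline in the SF-36 scores. Section 6.5.8 says "At study completion CRF page should be completed after the operation".

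**The concern.** Taken literally, the cross-reference sends an adverse event to a form built for hospital stays, whose contents go to a report separate from the main analysis. An event without an admission would have no form at all. The items named in Section 7.5.1 include neither severity nor device relatedness, yet Section 10.4.2 needs a relatedness judgement for its device-related summary. Section 7.4 does not fill the gap, because everything it lists belongs to the operation itself. No section in the available text says when adverse-event collection starts or stops.

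The schedule appears to compound this. A site working only from a table said to be complete would find no prompt for adverse events and none for a pre-operative SF-36. The second omission matters more: a questionnaire not completed before surgery cannot be recovered, and that patient would lose all 8 + 2 = 10 change scores (eight scales and two summary measures).

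The stakes are not trivial on paper. Section 10.3.1 describes the study as collecting primary evidence of safety and efficacy for a marketing submission, and the participants are healthy donors. Incomplete event capture would make the percentages in Section 10.4.2 too low.

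**Working it through.** The plan gives no figure to reproduce here, so the check is a comparison of sections.

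1. **Is the pointer wrong?** Yes. Section 7.5.2 cites 7.5.1 for adverse-event instructions, and 7.5.1 deals with hospital admissions. This holds on any reading.

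2. **Could a reader be misled about what is collected?** The literal reading puts adverse events in a resource-use report. Section 10.4.2 puts them in the main safety summaries. Both cannot hold, and only the second fits an adverse-event analysis. The reference is best read as a section number that was not updated.

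3. **Are the form and collection period missing from the plan?** The numbering goes from 7.5.2 to 10. Nothing in the available text names an adverse-event form or a period. If Sections 8 and 9 exist and hold those rules, only the wrong number remains. If they do not, a recording detail is unwritten, while the duty to record (7.5.2) and the summaries (10.4.2) still stand.

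4. **Does Section 6.5.8 end collection early?** No. It places the completion page after the operation, and week 26 is also after the operation. The same section speaks separately of withdrawing from follow-up. It sets no end date for adverse events.

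5. **Is a baseline SF-36 planned?** Three statements combine:
   - the questionnaire comes before the other assessments at a visit (7.5.2);
   - week 0 is visit 1 (schedule);
   - the analysis is change from baseline (10.4.4).

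   Together they require a questionnaire at visit 1. Section 7.2 does not mention it, but that section introduces its baseline information by example and does not claim to be exhaustive.

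6. **How much weight can the table bear?** Little. Its header is broken in the extracted text and its visit numbers run 1, 3, 4, 5. It also has no row for operative time or blood loss (secondary objectives in 3.2), for the satisfaction and recovery surveys in 7.3, or for the hospitalization data in 7.5.1. Nobody would conclude that operative time goes uncollected, and the same reasoning covers adverse events and the SF-36.

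7. **Can the effect be sized?** Two calculations suggest themselves, and neither measures the defect.
   - The longest interval between scheduled visits is 26 − 4 = 22 weeks, or 22/26 = 84.6% of follow-up. That is a gap between visits. An event in the interval can be reported at the next visit, and 7.5.1 already records follow-up hospitalizations, including those at other centres, for the duration of the study.
   - One patient whose only event went unrecorded would lower the any-event percentage by 1/20 = 5 points at the planned 20 patients. This is the weight of one patient in the sample. It says nothing about how often an event would be missed, and the documents give no rate.

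**The case for a change.** The strongest reply is that intention is not procedure. Section 10.4.2 says what will be tabulated, but tables need an event term and a relatedness judgement entered somewhere, and the available text names no form that holds them. The Hospitalization CRF would miss an event treated without admission. In a study of 20 healthy donors meant to support a marketing submission, a written form, a stated collection window and two schedule rows would cost almost nothing. A missed pre-operative SF-36 is beyond repair.

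Much of this is fair as a comment on drafting. The pointer is wrong, and the form and period are not stated in the text at hand. The step from there to lost data is not established. It requires a single centre, with three surgeons using the device, to follow one wrong section number and one incomplete table while disregarding Sections 7.5.2, 10.4.2 and 10.4.4. It also requires that no adverse-event rules exist in the unseen sections. The marketing purpose in Section 10.3.1 raises the standard of documentation one would like, but Section 10.1 keeps the analyses descriptive, so no test or decision threshold depends on this reference.

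**Conclusion.** The concern is right about the text and does not call for a change to the plan. It comes down to a clerical slip, a misnumbered cross-reference, together with documentation gaps that a study team would fill sensibly: schedule rows that are not marked, and a recording form and collection period not stated in the available text. Writing these down would improve the document without changing an endpoint, an analysis set, a summary or a result, and it offers no better method than the one already planned.

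The likely effect on the results cannot be quantified from the documents, and nothing in them indicates that it is more than negligible.

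This rests on two assumptions. The site works from the plan as a whole and not from the schedule alone. Adverse events named as safety variables in Section 10.4.2 are recorded during follow-up with enough detail to tabulate, including relatedness to the device. If it emerged that no adverse-event record was kept beyond hospital admissions, the second assumption would fail and the matter would need reopening. The available text does not show that.
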